#### 9.4.3 ANALYSIS OF THE SECONDARY ENDPOINT(S)

Secondary endpoints are independent of findings from the primary endpoint.

Rates of adverse events will be determined as a percentage of those subjects self-reporting an event compared to the total cohort following seven days of follow-up. Adverse events will be categorically expressed as a single endpoint. Difference in adverse events will be compared using Chi-squared test with incidence rates expressed as percentages. Analysis will be performed based on intention-to-treat. Missing data will be handled by last observation carried forward based on most recent self-reported adverse event (or lack thereof).

Rates of missed days of work or school will be determined as a percentage of those subjects self-reporting a missed day compared to the total cohort following seven days of follow-up. Missed days will be both categorically expressed as a single endpoint with incidence rates expressed as percentages as well as mean days missed with standard deviation. Difference in missed days will be compared using Chi-squared test for categorically expressed missed days (occurrence of any missed day(s) during study follow-up) and student's t-test for mean days missed. Analysis will be performed based on intention-to-treat. Missing data will be handled by last observation carried forward based on most recent self-reported missed day (or lack thereof).

Rates of seeking medical care including physician office visits or hospitalization for worsening respiratory illness will be determined as a percentage of those subjects self-reporting these events compared to the total cohort following seven days of follow-up. A physician office visit or hospitalization for worsening respiratory illness will be categorically expressed as a single endpoint with incidence rates expressed as percentages. Difference in need to seek medical care will be compared using Chi-squared tests. Analysis will be performed based on intention-to-treat. Missing data will be handled by last observation carried forward based on most recent self-reported medical visit (or lack thereof).

---

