### 5 STUDY POPULATION

#### 5.1 INCLUSION CRITERIA

In order to be eligible to participate in this study, an individual must meet all of the following criteria:

1. Provision of signed and dated informed consent form
2. Stated willingness to comply with all study procedures and availability for the duration of the study
3. Male or female, aged 18 years and older
4. Ability to take oral medication and be willing to adhere to the prescribed dosing regimen
5. Self-reported cold or flu symptoms for < 72 hours

Men and women of all ethnicities will be included.

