## 8.2 SAFETY AND OTHER ASSESSMENTS

Patients presenting to MUHC emergency department for cold and flu-like symptoms during the study period will be assessed for eligibility by the admitting physician based on protocol inclusion and exclusion criteria as previously detailed. Standard evaluation and collection of patient overall health status including past medical history, vital signs, physical exam, necessary imaging, and laboratory assessment will be completed as part of routine care associated with the emergency department visit. Patients enrolled into the study will be randomized and provided study drug the same day of their emergency department visit such that patients will not discharge from the emergency department until they have received their study drug and corresponding instructions for study participation. Testing results including COVID-19 status or positive influenza will be communicated via telephone contact to study patients as part of routine care follow-up and in accordance with MUHC emergency department

procedures. Patients meeting exclusion criteria following results of study related testing information will be instructed to discontinue study intervention and follow-up with their primary care provider or other non-study related healthcare provider for appropriate management.

Upon receiving study drug and following discharge from the emergency department study subjects will begin self-administering study product as outlined in section 6.1.2 of this protocol the evening of the day of enrollment. Research staff from the MUHC emergency department will begin contacting patients the following day and daily thereafter for a total of seven consecutive days as described in section 1.3 of this protocol. The following data elements are to be collected each day via telephone visits for the safety endpoints:

Safety endpoints:

Adverse Effect	Yes or No
nausea	
vomiting	
indigestion	
worsening of shortness of breath or difficulty breathing	
allergic reaction skin rash hives swelling of lips or tongue	
hospitalized or physician visit for study drug related adverse effect	

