### 8.3.4 TIME PERIOD AND FREQUENCY FOR EVENT ASSESSMENT AND FOLLOW-UP

The occurrence of an adverse event (AE) or serious adverse event (SAE) may come to the attention of study personnel during study visits and interviews of a study participant presenting for medical care, or upon review by a study monitor.

All AEs including local and systemic reactions not meeting the criteria for SAEs will be captured on the appropriate case report form (CRF). Information to be collected includes event description, time of onset, relationship to study product (assessed only by those with the training and authority to make a diagnosis), and time of resolution/stabilization of the event. All AEs occurring while on study must be documented appropriately regardless of relationship. All AEs will be followed to adequate resolution.

Any medical condition that is present at the time that the participant is screened will be considered as baseline and not reported as an AE. However, if the study participant's condition deteriorates at any time during the study, it will be recorded as an AE.

Study research technicians will record all reportable events via daily telephone visits with start dates occurring sometime near 24 hours after informed consent is obtained and continue until 2 days (for non-serious AEs and SAEs) after the last planned day of study drug administration (total of 7 days). At each study visit, study research technicians will inquire about the occurrence of AE/SAEs since the last visit. Events will be followed for outcome information until resolution or stabilization.

Solicited events will include patient self-reported:

- Nausea
- Vomiting
- Indigestion
- Worsening of shortness of breath or difficulty breathing
- Allergic reaction
  - skin rash
  - hives
  - swelling of lips or tongue
- Hospitalized or physician visit for study drug related adverse effect

Unsolicited events will include any patient self-reported adverse event that is provided without prompting by the research technician and that is not related/similar to any of the solicited events being collected.

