## 9.2 SAMPLE SIZE DETERMINATION

The target number of subjects to be enrolled during the study period occurring May 2022 – June 2023 is 100 (50 patients randomized to placebo and 50 to the supplementation group). This target is derived from a similarly conducted study evaluating zinc supplementation (without green tea extract) in a comparable adult population as identified with the current proposal. Based on an assumption that 60% of patients taking study drug and 30% in the placebo group would recover from cold and flu-like symptoms after five days of treatment a total of 84 patients would be sufficient to reach 80% power with a two tailed p value <0.05 to detect differences between groups. The power calculation was

$$N_1 = \left\{ z_{1-\alpha/2} * \sqrt{\bar{p} * \bar{q} * (1 + \frac{1}{k})} + z_{1-\beta} * \sqrt{p_1 * q_1 + (\frac{p_2 * q_2}{k})} \right\}^2 / \Delta^2$$

$$q_1 = 1 - p_1$$

$$q_2 = 1 - p_2$$

$$\bar{p} = \frac{p_1 + kp_2}{1 + K}$$

$$\bar{q} = 1 - \bar{p}$$

$$N_1 = \left\{ 1.96 * \sqrt{0.45 * 0.55 * (1 + \frac{1}{1})} + 0.84 * \sqrt{0.3 * 0.7 + (\frac{0.6 * 0.4}{1})} \right\}^2 / 0.3^2$$

$$N_1 = 42$$

$$N_2 = K * N_1 = 42$$

$p_1, p_2$  = proportion (incidence) of groups #1 and #2  
 $\Delta = |p_2 - p_1|$  = absolute difference between two proportions  
 $n_1$  = sample size for group #1  
 $n_2$  = sample size for group #2  
 $\alpha$  = probability of type I error (usually 0.05)  
 $\beta$  = probability of type II error (usually 0.2)  
 $z$  = critical Z value for a given  $\alpha$  or  $\beta$   
 $K$  = ratio of sample size for group #2 to group #1

performed using an online tool located at <https://clincalc.com/stats/samplesize.aspx> with the following calculations performed:

The anticipated dropout rate is 5% based on a large randomized control study evaluating safety of EGCG following 12 months of treatment using a similar daily dosage as the current proposal. No interim analysis is planned; power calculation is for primary endpoint only.

The primary outcome will be compared using the Chi-square test. Secondary outcomes will be assessed using the Chi-square test for categorical data and student's t-test for continuous data. An exploratory analysis comparing the primary outcome among COVID-19 only patients will also be conducted. All inferential testing will be based on intention-to-treat.

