### 9.4 STATISTICAL ANALYSES

#### 9.4.1 GENERAL APPROACH

Descriptive statistics for continues data will be expressed at means with standard deviations and categorical data will be expressed as percentage of total cohort. Inferential testing will use two-tailed p value <0.05 with 95% confidence intervals to determine statistical significance.

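### The daily safety form (8.2) and the adverse-event analysis (9.4.3) do not implement the baseline rule of 8.3.4, because no pre-dose status of the solicited symptoms is recorded

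*Combined protocol and SAP*

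**What the plan says.** **Entry.** Section 5.1 requires "Self-reported cold or flu symptoms for < 72 hours". None of the 13 exclusions in 5.2 names nausea, vomiting or indigestion. Influenza and COVID-19 are excluded only where specified treatment is current or planned.

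**Rule.** Section 8.3.4 says that a medical condition "present at the time that the participant is screened will be considered as baseline and not reported as an AE", with the exception that deterioration during the study is recorded as an adverse event. The same section has technicians ask what has occurred since the previous visit and puts time of onset on the case report form. It also contains the list of solicited symptoms.

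**Form.** Section 8.2 introduces its table with "The following data elements are to be collected each day via telephone visits for the safety endpoints". The items are Yes/No. Only the breathing item is worded as a worsening; nausea, vomiting, indigestion and the allergic signs carry no qualifier.

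**Timing.** Dosing starts on the evening of enrolment (6.1.2). The first call is the next day (8.2).

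**Baseline data.** The list in 9.4.5 has no gastrointestinal symptom, and the 12-symptom efficacy score in 8.1 has none either. Section 10.1.9.1 takes the baseline part of the case report form from 9.4.5.

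**Analysis.** Section 9.4.3: "Rates of adverse events will be determined as a percentage of those subjects self-reporting an event compared to the total cohort". All events form one any-event endpoint, tested by chi-square. Section 9.4.4 adds that each event counts once per subject. Neither section cites 8.3.4 or mentions new or worsened events.

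**The concern.** Take a patient who arrives nauseated, takes the first dose that evening and is still nauseated on the next day's call. Under 8.3.4 this is not an adverse event unless the nausea is worse. On the 8.2 form the truthful answer is Yes, and 9.4.3 as worded would include that patient. The plan does not say which reading governs, and no recorded starting state exists to settle it.

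Nausea is the most common side effect expected (2.3.1), and zinc may add to it. Section 9.1 hypothesises that adverse events will not be more frequent on the active product. Background symptoms counted equally in both arms push the result toward that conclusion, so the error would favour the answer the trial hopes for. A baseline not taken before the first dose cannot be reliably recovered afterwards.

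**Working it through.** **1. The plan's own figure.** The only sample-size figure is for recovery. The inputs in 9.2 are 60% vs 30%, 80% power and two-sided 0.05.

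n per arm = {1.96·√(0.45·0.55·2) + 0.84·√(0.3·0.7 + 0.6·0.4)}² / 0.3² = (1.379 + 0.563)² / 0.09 = 41.9, rounded up to 42

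The total is 84, as stated ("a total of 84 patients would be sufficient to reach 80% power with a two tailed p value <0.05"). Section 9.2 says the power calculation covers the primary endpoint only, so there is no adverse-event figure to reproduce.

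**2. Inputs for the adverse-event comparison.**
- 50 per arm (9.2).
- Two-sided 0.05: "Inferential testing will use two-tailed p value <0.05 with 95% confidence intervals to determine statistical significance" (9.4.1).
- Nausea 10.2% on EGCG vs 4.8% on placebo, from a 12-month trial (2.3.1).
- Nausea and stomach distress 13.5% on zinc vs 10.7% on placebo (2.3.1).
- b, the share of each arm with a solicited symptom at enrolment that is unchanged but counted. **This is an assumption**: the documents give no value. It is taken as equal in both arms, as randomisation gives in expectation.

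**3. Formula.** If r is the true rate of new events in an arm, the counted rate is b + (1 − b)·r. The risk difference therefore shrinks by the factor (1 − b), and the risk ratio moves toward 1. For example, at b = 10%:
- placebo: 0.10 + 0.90·0.048 = 14.3%
- active: 0.10 + 0.90·0.102 = 19.2%
- difference: 0.90·5.4 = 4.9 points
- ratio: 1.34

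**4. Results, EGCG nausea rates.** Power is exact for the two-sided Pearson chi-square test at 50 per arm, by enumerating both binomials.

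| b | Placebo | Active | Difference (points) | Risk ratio | Power |
|---|---|---|---|---|---|
| 0 | 4.8% | 10.2% | 5.4 | 2.1 | 16% |
| 5% | 9.6% | 14.7% | 5.1 | 1.54 | 13% |
| 10% | 14.3% | 19.2% | 4.9 | 1.34 | 10.5% |
| 20% | 23.8% | 28.2% | 4.3 | 1.18 | 8% |

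At the zinc rates, power is 7.5% at b = 0, 6.3% at 10% and 5.7% at 20%.

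**5. What the table shows.** The ratio is distorted quickly: a 5% share takes 2.1 to 1.54. The difference moves slowly. Power is poor before any dilution; by the normal approximation, 10.2% vs 4.8% needs 373 per arm for 80% power.

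**The case against.** The strongest reply is that 9.4.3 counts adverse events and 8.3.4 defines them. The solicited list sits inside 8.3.4, under the baseline rule. Technicians ask about occurrence since the last visit, time of onset is recorded, and 9.4.4 also records event dates. An onset before enrolment would identify an unchanged symptom, and the routine emergency-department history may mention it. Inclusion criterion 4 (able to take oral medication) and the exclusion of patients needing hospitalisation may keep out some who are actively vomiting.

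Most of this stands, and it limits the point. A reader might infer that the plan counts pre-existing symptoms and that the safety comparison is therefore diluted. The documents do not support that: they never say unchanged baseline symptoms are counted, and 8.3.4 says they are not adverse events. A reader might also infer that dilution costs the trial a well-powered safety test. It does not, because at the protocol's own rates power is about 16% and 7.5% with no baseline symptoms at all.

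The gap remains. Deterioration needs a starting state, and none is planned. The solicited table in 8.2 has no field for new versus continuing, and 9.4.3 makes no use of onset. No section makes the emergency-department history a study variable for these symptoms. Even if the adverse-event review in the schedule of activities is meant to begin on Day 1, 8.2 and 8.3.4 describe no solicited question before the first dose. Two analysts could both follow the protocol and report different adverse-event rates.

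**Conclusion.** The point holds as a gap in implementation: the form and the analysis do not carry out the rule in 8.3.4, and the data needed to judge deterioration are not planned. Dilution is a risk of unknown size, because b is not in the documents and 8.3.4, properly applied, would remove some or all unchanged symptoms. If a share of 5% to 20% were counted in both arms, a true risk ratio of 2.1 would be expected to appear as 1.54 to 1.18.

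The table rests on b being equal across arms and on every such case being counted. It also applies nausea-only rates from a 12-month trial to a seven-day any-event composite, so it illustrates direction and scale rather than forecasting the result. Background that is equal in expectation does not inflate type I error; it costs sensitivity. Correcting it makes the adverse-event rates interpretable and consistent with 8.3.4, but does not give the comparison adequate power.

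**What to change.** - **Enrolment, before the first dose:** ask every solicited item in 8.2 and record it as present or absent, with severity. The mild/moderate/severe scale in 8.3.3.1 could serve. Add these items to 9.4.5 so that they reach the case report form.
- **8.2:** word each daily item as new, or worse than at enrolment. Keep the plain Yes/No answer alongside so that the raw rate can still be tabulated.
- **9.4.3 and 9.4.4:** count only events that are new or worsened since enrolment, citing 8.3.4, and give the raw any-Yes rate by arm as supportive.

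The cost is a few questions at a visit already held in person, a revised call form and a sentence in each analysis section. The downside is that worsening is the participant's own judgement, so some misclassification will remain.

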## 2.3 RISK/BENEFIT ASSESSMENT

### 2.3.1 KNOWN POTENTIAL RISKS

Risk to study subjects is anticipated to be in accordance with those associated with using the study drug components individually. The most common side effect expected is nausea as a 12-month clinical trial evaluating EGCG against placebo using a dosing scheme similar to the current proposal found an incidence of 10.2% vs. 4.8%, respectively. Taking study drug two hours following a meal is expected to limit nausea, but residual risk cannot be eliminated altogether. Secondly, hepatotoxicity has been reported with EGCG supplementation, but risk is associated with treatment durations beyond 2-4 weeks and doses higher than 800 mg/day. Our protocol includes only five days of treatment at a dose of 800 mg/day thus liver injury is not an anticipated risk to patients. Furthermore, patients with a history of chronic liver disease will be excluded. Zinc supplementation at the proposed doses may also contribute to increased risk a nausea/vomiting. A case report of severe nausea and vomiting occurred in a 17-year-old male 30 minutes following an acute ingestion of 570mg elemental zinc; however, no other complications were observed. Clinical studies evaluating zinc lozenges for the treatment of cold and flu-like illness have reported increased incidence of gastrointestinal upset as compared to placebo. One such trial using a total daily elemental zinc dose up to 207mg observed a rate of nausea and stomach distress of 13.5% with zinc vs 10.7% that was associated with placebo. No studies of zinc lozenge therapy for cold and flu have reported any serious adverse effects, however, long-term use of zinc supplementation has been associated with copper and iron deficiency. Although the current protocol includes only five days of treatment patients with a history of copper or iron deficiency will be excluded.

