#### 9.4.4 SAFETY ANALYSES

Rates of adverse events including, nausea, vomiting, indigestion, worsening of shortness of breath or difficulty breathing, allergic reaction (skin rash, hives, swelling of lips or tongue), and hospitalized or physician visit will be included in secondary analysis as outlined in **Section 9.4.3**. Unsolicited adverse events recorded will be categorized as “other adverse events” and will be described as a incidence rate expressed as a percentage. Each adverse event recorded will be only counted once for any given study subject during the study follow-up period. The 10th revision of the International Statistical Classification of Diseases and Related Health Problems (ICD-10) codes will be used to code adverse events where appropriate. Severity of adverse events will be classified as follows:

- **MILD:** Awareness of signs or symptoms, but easily tolerated and are of minor irritant type causing no loss of time from normal activities. Symptoms do not require therapy or a medical evaluation; signs and symptoms are transient.
- **MODERATE:** Events introduce a low level of inconvenience or concern to the participant and may interfere with daily activities, but are usually improved by simple therapeutic measures; moderate experiences may cause some interference with functioning
- **SEVERE:** Events interrupt the participant's normal daily activities and generally require systemic drug therapy or other treatment; they are usually incapacitating

Expectedness of adverse events will be determined as follows:

- **UNEXPECTED** - nature or severity of the event is not consistent with information about the condition under study or intervention in the protocol, consent form, product brochure, or investigator brochure.
- **EXPECTED** - event is known to be associated with the intervention or condition under study.

Relatedness of adverse events will be determined as follows:

- DEFINITELY RELATED: The adverse event is clearly related to the investigational agent/procedure – i.e. an event that follows a reasonable temporal sequence from administration of the study intervention, follows a known or expected response pattern to the suspected intervention, that is confirmed by improvement on stopping and reappearance of the event on repeated exposure and that could not be reasonably explained by the known characteristics of the subject's clinical state.

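### Pooling every solicited adverse event into one tested percentage dilutes the nausea excess that the protocol itself expects; gastrointestinal intolerance needs its own comparison by arm

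*Combined protocol and SAP*

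**What the plan says.** Section 9.4.3 defines the adverse-event rate as the "percentage of those subjects self-reporting an event compared to the total cohort following seven days of follow-up". It continues: "Adverse events will be categorically expressed as a single endpoint". The comparison is: "Difference in adverse events will be compared using Chi-squared test with incidence rates expressed as percentages".

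Section 9.4.4 lists the content, "Rates of adverse events including, nausea, vomiting, indigestion, worsening of shortness of breath or difficulty breathing, allergic reaction", followed by hospitalization or physician visit. It states that these "will be included in secondary analysis as outlined in" Section 9.4.3. No test of a single item or of a gastrointestinal group is written. Section 9.4.4 also omits the restriction to visits for a drug-related effect, which Sections 8.2 and 9.1 attach to the same item.

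On direction, Section 2.3.1 says: "The most common side effect expected is nausea". Section 2.3.3 expects the nausea risk of the components to add up. Section 8.2 lists "worsening of shortness of breath or difficulty breathing" among the solicited items, which are collected one by one from the day after enrollment. Section 8.3.4 adds a baseline rule: "Any medical condition that is present at the time that the participant is screened will be considered as baseline and not reported as an AE".

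**The concern.** The items do not measure the same thing. Nausea, vomiting and indigestion are the tolerability questions for zinc and green tea extract. Worsening breathing can be a sign of the respiratory infection progressing. As Section 9.4.4 is worded, a medical visit can also be for the illness. When such items are pooled as any event, participants who already count because of an illness-related item cannot count again for nausea. The between-arm difference shrinks and the variance grows.

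At stake is the trial's only prespecified inferential comparison of tolerability. Section 9.1 hypothesizes that these events will not be more frequent on active. A diluted endpoint makes such a statement easier to reach while the harm that the protocol predicts is present.

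**Working it through.** **Check of the method on the plan's own figure.** The documents give no rate, margin or power for the adverse-event endpoint. The only sample-size figure is for recovery (Section 9.2: 60% vs 30%, 80% power, two-sided 0.05). The plan's formula gives {1.96·√(0.45·0.55·2) + 0.84·√(0.3·0.7 + 0.6·0.4)}² / 0.3² = (1.379 + 0.563)² / 0.09 = 41.9, so 42 per arm. This matches the plan. The same normal approximation is used below with 50 per arm.

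**Inputs.**
- Nausea 4.8% on placebo and 10.2% on active, from Section 2.3.1 (a 12-month placebo-controlled EGCG trial).
- A background, meaning the share of participants with at least one other item. The documents give none. I assume it is equal in both arms and show 30% and 50%.
- Nausea and the other items are treated as independent (assumption).

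**Dilution with no drug effect on the other items.** Pooled rate = 1 − (1 − background)(1 − nausea).
- Nausea alone: 4.8% vs 10.2%, difference +5.4 points.
- Background 30%: placebo 1 − 0.7·0.952 = 33.4%; active 1 − 0.7·0.898 = 37.1%; difference 0.7·5.4 = +3.8 points.
- Background 50%: placebo 1 − 0.5·0.952 = 52.4%; active 1 − 0.5·0.898 = 55.1%; difference +2.7 points.

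An equal background multiplies the difference by (1 − background).

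**Power at 50 per arm.** Power = Φ{[Δ√50 − 1.96·√(2·p̄·(1 − p̄))] / √(p₁q₁ + p₂q₂)}.
- Nausea alone: (0.054·7.071 − 1.96·0.3725) / 0.3705 = −0.94, so 17%.
- Pooled with 30% background: (0.0378·7.071 − 1.96·0.6756) / 0.6751 = −1.57, so about 6%.
- For a larger, assumed gastrointestinal difference of 10% vs 30%: 71% alone. Pooled with a 20% equal background (28% vs 44%): 38%.

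**What masking would require.** Suppose the only other item is worsening breathing, and the product reduces it. The active-arm breathing rate that exactly cancels the nausea excess is 1 − 0.952·(1 − placebo rate) / 0.898. The placebo rates are assumptions:

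| Placebo rate (assumed) | Cancelling active rate | Relative reduction |
|---|---|---|
| 10% | 4.6% | 54% |
| 20% | 15.2% | 24% |
| 30% | 25.8% | 14% |
| 40% | 36.4% | 9% |

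For the assumed 10% vs 30% gastrointestinal difference, cancellation from a 30% placebo breathing rate would need a fall to 10%.

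**What the separate comparison can deliver.** At 4.8% vs 10.2% the expected counts are 0.048·50 = 2.4 and 0.102·50 = 5.1 participants. The 95% half-width of the risk difference is 1.96·√[(0.048·0.952 + 0.102·0.898)/50] = 10.3 points, around +5.4. A test with 80% power would need 373 per arm.

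**The case against.** **The text may not mean a composite.** The single-endpoint wording recurs in the plan. For missed days it means that seven daily answers collapse into one yes/no. Section 9.4.4 counts each adverse event once per participant, which fits a count by event type. This stands in part: a per-item reading is possible. But Section 9.4.3 counts participants with an event and plans one test, and no per-item test is written, so the pooled reading remains the natural one.

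**The illustration is favorable to the point.** It gives a drug excess to nausea only and places vomiting and indigestion in an equal background. Section 2.3.1 says zinc may raise both nausea and vomiting, so the true gastrointestinal excess could be larger and harder to hide. This stands, and so the figures are illustrations rather than forecasts.

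**A reader might infer that the components are bound to move in opposite directions and cancel.** The documents do not support that. They give no rate of worsening breathing and nowhere predict a reduction in it. Shortness of breath is not among the 12 scored symptoms.

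**A reader might also infer that someone who arrives vomiting is counted as an event.** Section 8.3.4 excludes conditions present at screening, and history and examination are recorded at the enrollment visit. What remains is that no pre-dose checklist of the same items is stated, so persisting symptoms can be miscounted, in both arms.

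**Item-level data are not lost.** Section 8.2 collects the items separately and Section 9.4.8 tabulates data by measure. This is correct. What is missing is a prespecified by-arm comparison with intervals.

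**Low power would limit a separate test too.** This also stands, and it is why intervals matter more here than a p-value.

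**Conclusion.** The point holds as a weakness in the prespecified safety comparison. Read most naturally, Sections 9.4.3 and 9.4.4 test one pooled percentage, which dilutes the harm that the protocol expects. At the cited nausea rates, the +5.4 points shrink to +3.8 with a 30% equal background and to +2.7 with 50%. These sizes rest on independence and on assumed backgrounds; the direction of the dilution does not depend on the level chosen. Complete masking is possible but depends on a benefit on breathing for which the documents give no figure, so it is not part of the conclusion. Separating the gastrointestinal events removes the dilution but does not make 50 per arm adequate to detect a difference of the cited size.

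**What to change.** - In Section 9.4.3, compare gastrointestinal intolerance (any of nausea, vomiting or indigestion) by arm as its own safety comparison.
- Report every solicited event, including worsening breathing, by arm with a risk difference and 95% confidence interval. Keep worsening breathing among the adverse events, since it can also be drug- or allergy-related.
- Label the pooled any-event percentage as descriptive.
- In Section 9.4.4, restore the drug-related restriction on medical visits so that it agrees with Sections 8.2 and 9.1.
- State that a non-significant difference will not be read as showing that events are no more frequent.
- Optionally, record the same items before the first dose so that the baseline rule in Section 8.3.4 can be applied consistently.

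The cost is a few sentences in the analysis section, some table rows and, if adopted, a short checklist at the existing enrollment visit. The downside is several comparisons in place of one, each with a wide interval at 50 per arm.
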